#### **7.7 Multiple Comparisons**

This study has only one primary endpoint, so no multiplicity issues are present.

For the secondary endpoints, no adjustment will be made to the significance level to account for multiple testing.

## 7.8 Planned Subgroups, Interactions and Covariates

The following exploratory subgroup analyses of the primary endpoint are planned in the FAS:

- Age at hospital admission: <65 years;  $\geq$  65 years
- Gender: male; female
- Time to ROSC: < 25min;  $\geq$  25 min
- Initial rhythm: shockable; not shockable
- Bystander CPR: yes; no
- Presence of chronic hypertension: yes; no
- Study site: UZ Leuven; ZOL-Genk

Summary statistics per treatment and estimated treatment differences, obtained using ANOVA, will be presented for each subgroup. In addition, the interaction between the above subgroups and randomized treatment will be tested to assess whether the treatment effect differs according to subgroup.

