4. INTRODUCTION

4.1. The clinical problem

There is absolutely no doubt that sudden cardiac death is a major problem in Belgium in terms of numbers of patients, medical impact and socio-economic impact. Each day, approximately 30 adults suffer from an unexpected out-of-hospital cardiac arrest in Belgium, a number exceeding the incidence of breast or prostate cancer with an estimated 25 new patients per day in Belgium. In addition, many cardiac arrest patients are young (mean age in our hospital 60±12 years, 56% of patients younger than 65 years) with a large economic potential for society. In the community, the occurrence of sudden death often takes center stage through highly mediatised cases of cardiac arrest in young sportsmen with or without a previously undiscovered cardiac anomaly. Apart from the traumatic experience of these dramatic sudden events, only 40% of patients that reach the hospital with spontaneous circulation survive without major neurological impairment or care dependency. An additional 5-10% of the cohort survives with major neurological impairment including a permanent vegetative state. These sobering outcome data and the large economic burden for society (estimated cost of a nursing home facility for these patients approximately 30-50000 €/year) mandate novel treatment strategies that could improve prognosis after cardiac arrest.

Apart from temperature management to avoid fever, no single in hospital randomized controlled intervention trial has improved outcome of these patients. In this way, there is absolutely no doubt that a positive result of the Neuroprotect post-CA trial would be a clear added value for this vulnerable and highly under-investigated patient group.

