Censored outcomes will be presented using Kaplan-Meier curves analyzed using a stratified long-rank test. The treatment effect will be expressed as a hazard ratio.

Prespecified subgroup analysis

Prespecified subgroup analysis will be performed for the primary endpoint according to age (> or <65 years), gender, time-to-ROSC (> or < 25 min), Initial rhythm (shockable or non-shockable), presence of bystander CPR (yes/no), presence of chronic hypertension (yes/no) and treatment center.

The interaction will be assessed using an analysis of variance.

The full statistical methods planned for this trial will be written as a separate document (Statistical Analysis Plan) prior to the completion of the study.

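### The age and time-to-ROSC interactions are tested only on two-category splits; adding continuous terms would recover information at almost no cost

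*SAP*

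**What the plan says.** SAP 7.8 introduces the list with "The following exploratory subgroup analyses of the primary endpoint are planned in the FAS". Two of the seven factors are continuous by nature but appear only as two categories: "Age at hospital admission: <65 years" against 65 and over, and "Time to ROSC: < 25min" against 25 minutes and over. The SAP then states that "the interaction between the above subgroups and randomized treatment will be tested to assess whether the treatment effect differs according to subgroup". The interaction test therefore uses the categories.

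Protocol 6.9.3 has the same cuts, "according to age (> or <65 years), gender, time-to-ROSC (> or < 25 min", and adds: "The interaction will be assessed using an analysis of variance". Neither document gives a reason for 65 years or for 25 minutes.

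Protocol 6.4 lists age and time to ROSC among the baseline data, with no categories attached. The SAP itself uses age, not an age group, in the imputation model (7.4), and section 10.2.3 reuses those covariates in the survival model for the SF-36 analysis. No section plans a treatment-by-continuous-age or treatment-by-continuous-time term.

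**The concern.** A split at 65 treats patients aged 64 and 66 as different and patients aged 30 and 64 as alike. If a modifier acts gradually, the test ignores information that the trial already holds.

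The trial is sized for an average treatment effect, so its interaction tests start with limited power. Coding two of them less efficiently makes it more likely that a real gradual change in effect goes undetected. What is at stake is the usefulness of two exploratory analyses, not the primary conclusion.

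**Working it through.** **Inputs from the documents**
- Age (Protocol 4.1, own hospital): "mean age in our hospital 60±12 years, 56% of patients younger than 65 years".
- SD of the primary endpoint 8.9 points, 56 per arm, 80% power, two-sided 0.05 (SAP 5); 112 patients in total (Protocol synopsis).
- Time to ROSC: no mean, median, SD or percentile is given anywhere.

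**Step 1. The plan's own figure.** The documents state no power for the interactions, so only the sample size can be checked. The difference detectable with 56 per arm is 8.9 × √(2/56) × (1.96 + 0.84) ≈ 4.71 points. A 40% reduction then implies a control mean of 4.71/0.40 ≈ 11.8%. The documents do not state that mean, so the 56 is consistent with it but cannot be confirmed. The 4.71 points serve below as a yardstick.

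**Step 2. Information kept by the age split.** Assume a normal modifier and a treatment effect linear in it. A split with share p below the cut keeps φ(z)²/[p(1−p)] of the information, where z is the normal quantile of p.
- From 56% below 65: 0.631 kept, 37% lost.
- From mean 60 and SD 12: z = (65−60)/12 = 0.417 and p = 0.66; 0.598 kept, 40% lost.

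The two differ because the protocol's figures do not fit a normal distribution exactly (66% implied below 65, 56% stated). Hence the range of 37-40%. It is as if the interaction were tested on 0.598 × 112 ≈ 67 to 0.631 × 112 ≈ 71 patients.

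**Step 3. Time to ROSC (assumed distributions only)**

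| Assumption | Information lost |
|---|---|
| Normal, 50/50 split | 36% |
| Normal, 70/30 split | 42% |
| Normal, 80/20 split | 51% |
| Lognormal, median 15-30 min, log-SD 0.4-0.8, effect linear in minutes | 38% to 69% |

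These are scenarios, not estimates for this trial. A flatter distribution would lose less.

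**Step 4. Power of the age interaction.** This was simulated with N=112, 1:1 allocation, age normal (60, 12), residual SD 8.9, complete data and 4,000 runs per row.

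| True modification by age | Continuous | Split at 65 |
|---|---|---|
| Linear, 4.71 points per SD | 78% | 54% |
| Linear, 2.355 points per SD | 27% | 18% |
| Step of 4.71 points at 65 | 17% | 26% |
| Step of 9.42 points at 65 | 50% | 74% |

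A hand check of the linear rows: the standard error of the slope is 2 × 8.9/√112 = 1.68. For the larger slope, 4.71/1.68 = 2.80, and Φ(2.80 − 1.96) ≈ 80%. With the split, √0.598 × 2.80 = 2.17, and Φ(2.17 − 1.96) ≈ 58%. For half the slope the same steps give about 29% and 19%. The simulation is slightly lower, as expected: it uses the t distribution, and with the split the unmodelled part of the slope adds to the residual. A separate run with n=109 (112 less the three patients excluded from the FAS in SAP 6.2) gave type I error of 4.5% for the continuous test and 4.8% for the split.

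**The case against.** Several objections carry weight.

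- **The direction depends on the shape of the effect.** If the effect changes abruptly at the cut, the split is clearly the better test, as the last two rows show. The documents support neither a gradual change nor a threshold. This stands, and it is why the continuous term should be added and not substituted.
- **The large-slope scenario is extreme.** A slope of 4.71 points per SD equals the whole average effect for which the trial is sized. The benefit would vanish 12 years to one side of age 60 and double 12 years to the other. At half that slope both tests have little power. This stands.
- **Missing MRI data.** SAP 10.1 expects a substantial share of missing values, and the simulation has none. The imputation model in SAP 7.4 lists neither time to ROSC nor any treatment-by-modifier product. If the subgroup analyses use imputed data, which 7.8 does not say, the interactions would tend to be diluted under either coding. The fix below does not address this.
- **Prespecified cuts have value.** They prevent a data-driven choice, and they stand in the protocol. This argues for keeping them. It does not argue against a second, equally prespecified term.
- **Exploratory status.** No claim or error rate depends on these tests. This limits the importance of the point but does not remove it, since the better use of the data needs no new data.

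A reader might infer that the plan discards about 40% of the information on both modifiers, whatever the shape of the effect. The documents do not support that: the figure is for age, is conditional on normality and linearity, and has no counterpart for time to ROSC. A reader might also infer that a non-significant interaction will be reported as proof of a uniform effect. SAP 7.8 does not say so.

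**Conclusion.** The point holds as a modest improvement. Both interactions are planned only on two-category splits although both variables are collected at baseline. For age, the loss is about 37-40% of the information, provided that age is roughly normal, that the effect is linear in age, and that the single-hospital age figures apply to the trial population. For time to ROSC, the size is unknown.

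The practical gain in power for age runs from about 9 points (27% against 18%) to about 24 points (78% against 54%) in the two linear scenarios, with complete data. It becomes a loss if the effect steps at the cut. The primary analysis, its error rate and its interpretation are not affected.

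**What to change.** In SAP 7.8, keep the splits, their tables and their interaction tests as prespecified. Add one paragraph, fixed before unblinding:

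- Fit treatment × age with age continuous, and in a separate model treatment × time to ROSC with time continuous. Include the main effects and shockable rhythm in each.
- State in advance the scale for time to ROSC, for example logarithmic.
- Add a simple check for non-linearity of each interaction.
- Report the estimated treatment effect with its 95% interval at, for example, the quartiles of each variable.

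The cost is a short SAP text, two extra models and a documented change under Protocol 6.10. The downside is two more exploratory tests, and a linear term that has less power than the split if the effect truly steps at the cut; the retained split tests cover that case. If treatment codes have already been opened, the added terms should be labelled post hoc.

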### 3 Study Methods

#### 3.1 Overall Study Design and Plan

This was a prospective, multicentre, interventional, controlled, randomized, open-label investigator-driven study.

Patients were recruited at 2 tertiary care hospitals in Belgium (UZ Leuven and ZOL-Genk) and were randomized in a 1:1 ratio to either goal-directed hemodynamic optimization or standard care. In patients randomized to receive the intervention, the target mixed venous oxygen saturation (SVO2) was between 65-75% and the target mean arterial pressure (MAP) was between 85- 100mmHg. Fluid administration and hemodynamic support was adjusted according to a flow chart in case SVO2 or MAP were below or above the suggested targets on an hourly basis. The intervention lasted up to 36 hours after admission to ICU.

Once admitted to ICU, the patients were assessed hourly up to 36 hours after admission and daily up to 5 days after admission. Further assessments were done at discharge from ICU, discharge from the hospital and at 180 days after the initial cardiac arrest.

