## 5 Sample Size Determination

Based on the results of a pilot study at Stanford University in which the standard deviation of the percentage  $ADC < 0.650 \text{ mm}^2/\text{s}$  in comparable post-CA patients was 8.9%, it was estimated that 56 patients would be necessary in each study group to show a 40% reduction in the extent of cerebral ischemia with a power of 80% at a two-sided alpha level of 0.05.

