#### **7.4 Methods for Withdrawals, Missing Data and Outliers**

For the primary endpoint, multiple imputation methodology will be used to account for missing data. A total of 100 imputations will be done. The imputation model will include the following:

Age, gender, presence of bystander CPR, presence of initial shockable rhythm, neuron specific enolase at days 1-2-3-4-5, presence of a malign EEG pattern on Day 1 and allocated treatment and death within 7 days of randomisation.

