## 10 Primary and Secondary Endpoints

### 10.1 Primary Endpoint

The primary endpoint will be summarised by randomised treatment group.

Since it is expected that a substantial proportion will have missing data for the primary endpoint (due to early mortality or other reasons), a statistical analysis that does not take account of this missingness is very likely to be subject to considerable bias.

Therefore, missing primary endpoint data will be imputed using the imputation model described in section 7.4.

In each imputation sample, the data will be analysed using an ANOVA that includes a factor for randomised treatment and the stratification factor of shockable rhythm. The results of the analyses will then be combined with standard methodology, using SAS PROC MIANALYZE.

The effect of randomised group will be estimated by the difference between groups and presented along with its associated 95% confidence interval.

The statistical analysis of the primary endpoint will be performed for the FAS and PPS.

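### The imputation model in SAP 7.4 holds no treatment-by-subgroup terms, so the exploratory interaction tests in SAP 7.8 can be pulled toward zero if, as seems intended, they use the imputed endpoint

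*SAP*

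**What the plan says.** SAP 7.8 lists exploratory subgroup analyses of the primary endpoint in the FAS: age, gender, time to ROSC, initial rhythm, bystander CPR, chronic hypertension and study site. Beyond estimates within subgroups, "the interaction between the above subgroups and randomized treatment will be tested to assess whether the treatment effect differs according to subgroup". ANOVA is named as the method. The section does not say which data the ANOVA is run on.

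SAP 10.1 states that "it is expected that a substantial proportion will have missing data for the primary endpoint (due to early mortality or other reasons" and warns that ignoring this would probably bias the analysis considerably. SAP 7.4 therefore says that for the primary endpoint "multiple imputation methodology will be used to account for missing data. A total of 100 imputations will be done". Its list of predictors opens with age, gender, bystander CPR, initial shockable rhythm and NSE on days 1 to 5, and ends with "presence of a malign EEG pattern on Day 1 and allocated treatment and death within 7 days of randomisation".

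Four of the seven subgroup variables are thus in the imputation model, as main effects only (age, gender, bystander CPR, rhythm). Three are absent (time to ROSC, chronic hypertension, site). No interaction with treatment and no imputation by arm is mentioned. The shorter imputation list in Protocol 6.9.3 also contains no hypertension, site or interaction term.

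**The concern.** An analysis model should not ask for a contrast that the imputation model assumes to be absent. Here the ANOVA tests treatment by subgroup, while the missing endpoint values are drawn from a model with one treatment effect common to all subgroups. The imputed patients then contribute little or none of any real interaction, and the pooled estimate is diluted.

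What is at stake is interpretation. A non-significant interaction from a diluted, over-conservative test may be read as evidence that the effect is consistent across subgroups. Chronic hypertension is a subgroup where a difference is plausible on the protocol's own account: Protocol 4.3 links it to a rightward shift of autoregulation. It is one of the three variables left out.

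**Working it through.** **Inputs from the documents.** SAP 5: the SD of the endpoint "in comparable post-CA patients was 8.9" percentage points, and "it was estimated that 56 patients would be necessary in each study group" to detect a "40% reduction in the extent of cerebral ischemia with a power of 80% at a two-sided alpha level of 0.05". SAP 3.1: patients "were randomized in a 1:1 ratio to either goal-directed hemodynamic optimization or standard care". SAP 6.2: three patients excluded from the FAS. With the 112 planned, this gives an assumed FAS of 112 - 3 = 109.

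**Assumed, because the documents give no figure.** Missing share m of 20-40%; true interaction of -8 points; treatment effect of -4.7 points in the reference subgroup; subgroup split 50/50; correlation R between the auxiliaries and the endpoint of 0 to 0.7.

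**Step 1. The plan's own figure.** The detectable difference is d = sqrt(2 × (1.96 + 0.84)² × 8.9² / 56) = 4.71 points. A 40% reduction then implies a control mean of 4.71 / 0.40 = 11.8%. The plan does not state the control mean, so 56 per group is consistent with the stated inputs but cannot be reproduced independently (a control mean of 11% would need 65, 12% would need 54 and 13% would need 46).

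**Step 2. Why the interaction shrinks.** In each treatment-by-subgroup cell the completed mean is (1 - m) × observed mean + m × imputed mean. If the imputed means carry a fraction R² of the interaction through the auxiliaries, then

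estimated interaction = true interaction × [1 - m × (1 - R²)].

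With R = 0 and equal missingness across cells, the shrinkage equals m.

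**Step 3. Numbers for a true interaction of -8.**

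| Missing | R = 0, formula | R = 0, simulated | R = 0.5 to 0.7, formula | R = 0.5 to 0.7, simulated | Interaction imputed, R = 0, simulated |
|---|---|---|---|---|---|
| 20% | -6.4 | -6.42 | -6.8 to -7.2 | -6.6 to -7.0 | -7.90 |
| 30% | -5.6 | -5.53 | -6.2 to -6.8 | -6.0 to -6.5 | -8.01 |
| 40% | -4.8 | -4.83 | -5.6 to -6.4 | -5.1 to -6.2 | -7.99 |

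The formula is a guide. The simulated values with informative auxiliaries lie somewhat further from -8, but the pattern is the same.

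**Step 4. Main effects alone do not help.** With the subgroup variable in the imputation model but not its interaction, the ratios to the truth are 0.80, 0.70 and 0.59 at 20, 30 and 40% missing. The four subgroup variables already listed in 7.4 are therefore affected as well.

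**Step 5. With an NSE-like auxiliary and early death in the model.** At 32% missing the shrinkage is 29, 27, 21 and 14% for R = 0, 0.3, 0.5 and 0.7. Divided by 32%, this is about 90, 83, 66 and 45% of the missing share.

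**Step 6. Unequal missingness.** If missingness is three times higher in one subgroup level, the ratio at 40% missing falls to 0.53, a little worse than the missing share. If it varies by subgroup and arm and the omitted variable is prognostic (assumed effect of 6 points), a false interaction of about 0.5 to 1.0 points can appear.

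**Step 7. The test.** With R = 0 the estimate is (1 - m) times the observed-case estimate, so its true variance is about (1 - m) times the full-data variance. The combined variance reported after imputation is at least the full-data variance. Type I error is therefore at most the chance that a standard normal exceeds 1.96 / sqrt(1 - m) in absolute value: 2.19, 2.34 and 2.53, or 2.8, 1.9 and 1.1%, at 20, 30 and 40% missing. Simulation at n = 109 gives 0.7, 0.7 and 0.1%. Power for -8 is 34, 21 and 7%, against 51, 46 and 43% when the interaction is imputed.

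**The case against.** Four points can be made for the plan, and each limits the concern.

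- **Data source.** A reader might infer that SAP 7.8 prescribes imputed data. It does not say so. If observed scans alone were used, this shrinkage would not arise. That reading brings in the bias SAP 10.1 warns of, and silence on the choice is itself a gap. The shrinkage nevertheless depends on the reading.
- **Post-randomisation auxiliaries.** A reader might infer that imputed patients carry no interaction at all, so that the loss equals the missing share. NSE, EEG and early death come after randomisation and can transmit part of a real interaction. The missing share is therefore roughly the upper end when missingness is similar across cells, and the documents do not allow one figure.
- **Size against noise.** No document gives an interaction of -8, which is 8 / 4.71 = 1.7 times the effect the trial was sized for. With 109 patients in four equal cells the standard error is 8.9 × sqrt(4 / 27.25) = 3.4 points with complete data, and about 4.1 at 30% missing. The loss at 30% missing, about 2.4 points, is below one standard error, and power after the fix is still only 43-51%. This stands: the fix removes a systematic bias but does not make the tests powerful.
- **Importance.** The subgroups are labelled exploratory. It would be tempting to call hypertension central to the trial's hypothesis, but Protocol 4.3 reports it as a correlate of shifted autoregulation and takes the autoregulation-based pressure range from all 51 patients pooled. No objective concerns hypertensive patients.

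What remains is the mismatch itself: seven interactions are tested, none is in the imputation model, and the dilution is generally toward no interaction.

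**Conclusion.** The point holds as a low-cost improvement to an exploratory analysis. On the natural reading of SAP 7.4, 7.8 and 10.1, interaction estimates can be pulled toward zero by up to about the missing share, or roughly 45-90% of it when an NSE-like auxiliary and early death are in the model. The tests then reject a true null in about 0-3% of trials instead of 5%.

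The point-scale figures rest on an assumed interaction of -8, the SD of 8.9 from SAP 5, an even subgroup split and assumed missing shares of 20-40%. They illustrate the mechanism and do not predict what this trial will show. Markedly unequal missingness could make the shrinkage somewhat larger, or create a small false interaction. The documents do not support extending the point to the primary treatment comparison, which contains no subgroup interaction and is unaffected by it.

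**What to change.** State in SAP 7.8 that the subgroup analyses use multiply imputed data. For each subgroup analysis, impute from the 7.4 model plus that subgroup variable, where it is not already listed, plus its interaction with treatment, one subgroup at a time. Leave the imputation for the primary analysis as it is. In simulation this recovers 0.99-1.00 of the true interaction and brings type I error back to about 5%.

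Imputing separately by arm with the subgroup variable included would also allow the interaction. However, it means fitting five NSE days and the other predictors to about 109 / 2 ≈ 55 patients per arm, fewer of them with scans, and may be unstable. One interaction at a time is preferable.

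No new data are needed: time to ROSC and medical history are baseline items in Protocol 6.4, and site is known. The costs are up to seven extra imputation runs, somewhat wider intervals, and completed data that may differ slightly from those of the primary analysis, so overall effects behind the subgroup tables need not match the primary result exactly. A footnote to the subgroup tables should say so.
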